5.7.5. Vital Signs and Physical Examination

The selected vital signs parameters, performed at scheduled or unscheduled visits, will be analyzed to determine the incidence of abnormalities using the criteria listed in [Table 4](#).

The percentages will be calculated relative to the number of participants with at least 1 post-baseline value for the specific vital sign (except Weight for which it would be participants with both baseline and post-baseline assessments). The numerator is the total number of participants with at least 1 post-baseline abnormal value.

Table 4: Criteria for Potentially Clinically Significant Vital Signs

Vital Sign Parameters	Criteria
Temperature	<36 degrees C >38 degrees C
Pulse	<60 bpm >100 bpm
Systolic blood pressure	<90 mmHg >140 mmHg >160 mmHg
Diastolic blood pressure	<50 mmHg >90 mmHg >100 mmHg
Weight	7% or more increase from baseline 7% or more decrease from baseline
Respiratory Rate	<12 breaths/min >20 breaths/min

In addition, summary statistics for actual values and change from baseline will also be presented for all quantitative vital sign parameters. These tables will be presented for each cohort and overall. Participants with abnormal vital signs data will be included in the listings.

Abnormal new or worsening findings that occurred during or after administration of study treatment and are deemed by the Investigator as clinically significant will be reported as AEs and included in AE analysis, findings that occurred prior to administration of study treatment should be reported under medical history and included in the medical history analysis.

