⁵ Full physical examination at Screening. Brief physical examination, symptom-directed, at all other visits.

⁶ To confirm postmenopausal status (in postmenopausal female participants only).

⁷ To be performed only in women of childbearing potential; results must be negative to continue participation in study.

⁸ Samples for serum pregnancy test are to be analyzed by the central laboratory. Results must be known prior to study treatment distribution.

⁹ Samples for urine pregnancy test are to be analyzed by the local laboratory.

¹⁰Laboratory assessment as per Table 5.

¹¹Intensive PK samples will be collected in a subset of PK population (n = 7 Japanese cohort only) at any timepoint in the period between Week 4 (Day 29, Visit 3 ± 3 days) and Week 24 (Day 169, Visit 8 ± 5 days), both inclusive; see the PK sampling timepoints in Table 6.

¹²In both Japanese and Chinese participants, on Days 29 and 57, PK samples will be taken -30 to 0 minutes predose and approximately 2 to 3 hours postdose for those participants whose intensive PK samples are not collected on this day (non-PK population).

[figure not shown]
¹³No intense PK sampling will be conducted in Chinese MS participants. Chinese MS participants will have sparse PK on Days 29 and 57.

CONFIDENTIAL

The information contained herein may not be used, disclosed, or published without the written consent of Biogen MA Inc.

¹⁴In the event that a participant is enrolled in both the sparse and intensive PK cohorts and intensive PK sampling was completed on Day 29 or Day 57 for a participant, sparse PK sampling will not be required for said days. However, if it is determined that intensive PK is not feasible by Day 57, sparse PK sampling will be completed according to protocol and intensive PK should be completed at later visits.

¹⁵Vital sign measurements include temperature, respiratory rate, blood pressure, and pulse rate. Blood pressure, respiratory rate, and pulse rate will be measured after the participant has been in a seated or supine position for at least 5 minutes.

¹⁹Use the "Baseline Screening" version at Screening; use the "Since Last Visit" version at all other scheduled visits.

CONFIDENTIAL

The information contained herein may not be used, disclosed, or published without the written consent of Biogen MA Inc.

Table 2: Additional Follow-Up for Participants with Lymphopenia

Assessments	LM Visits ¹		

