6.2. Exclusion Criteria

Medical History and Current Health Status

CONFIDENTIAL

The information contained herein may not be used, disclosed, or published without the written consent of Biogen MA Inc.

1. Has an MS relapse that has occurred within the 30 days prior to randomization and/or the participant has not stabilized from a previous relapse prior to randomization.
2. History of any clinically significant cardiac, endocrinologic, hematologic, hepatic, immunologic, infectious, metabolic, urologic, pulmonary, neurologic, dermatologic, psychiatric, and renal or other major disease that would preclude participation in a clinical trial, as determined by the Investigator.
3. History of severe allergic or anaphylactic reactions or of any allergic reactions that, in the opinion of the Investigator, are likely to be exacerbated by any component of the study treatment.
4. History of, or ongoing, malignant disease, including solid tumors and hematologic malignancies (with the exception of basal cell carcinomas and squamous cell carcinomas of the skin that have been completely excised and considered cured at least 1 year prior to Day -1). Participants with cancers in remission for greater than 5 years prior to Baseline Visit (Day 1) may be included after discussion with/approval by the Sponsor.
5. Has a history of GI surgery (except appendectomy or cholecystectomy that occurred more than 6 months prior to Screening), irritable bowel syndrome, inflammatory bowel disease (Crohn's disease, ulcerative colitis), or other clinically significant and active GI condition per the Investigator's discretion.
6. History of clinically significant recurring or active GI symptoms (e.g., nausea, diarrhea, dyspepsia, constipation) within 90 days of Screening, including symptoms that require the initiation of symptomatic medical treatment (e.g., initiation of a medication to treat gastroesophageal reflux disease) or a change in symptomatic medical treatment (e.g., an increase in dose) within 90 days prior to Screening.
7. Participant has a mental or physical condition that would preclude performing [REDACTED] and safety assessments.
8. Systolic blood pressure > 150 mmHg or < 90 mmHg after sitting for 5 minutes at Screening or prior to dosing. If out of range, testing may be repeated once at Screening and once prior to dosing. Participants must not be dosed if the repeated value is still out of range.

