9. Participant has second- or third-degree atrio-ventricular block or sick sinus syndrome, uncontrolled atrial fibrillation, severe or unstable angina, congestive heart failure, myocardial infarction within 3 months of the Screening visit, or significant ECG abnormality, including QTc > 450 msec (males) or 470 msec (females), where QTc is based on Fridericia's correction method.
10. Plans to undergo elective procedures or surgeries at any time after signing the ICF through the Follow-Up Visit.
11. Any condition affecting study treatment absorption (e.g., gastrectomy).

CONFIDENTIAL

The information contained herein may not be used, disclosed, or published without the written consent of

Biogen MA Inc.

12. History of sensitivity to heparin or heparin-induced thrombocytopenia.
13. History of systemic hypersensitivity reaction to DRF, DMF, MMF or other fumaric esters, the excipients contained in the formulation, and if appropriate, any diagnostic agents to be administered during the study.
14. Participant has an abnormality that the investigator deems to be clinically significant on medical history, physical examination, ECG, or a diagnostic laboratory test that may confound study results or pose risk to the subject through participation in the study, in the opinion of the Investigator.

Infection Risk

15. Evidence of current SARS-CoV-2 infection within 14 days prior to Screening, between Screening and Baseline Visit (Day 1), or at Baseline Visit (Day 1), including but not limited to a fever (temperature $> 37.5^{\circ}\text{C}$), new and persistent cough, breathlessness, or loss of taste and/or smell.

Note: If a SARS-CoV-2 test (PCR or other regulatory approved method) is performed per the discretion of the Investigator in accordance with local site practice, the test result must be negative in order for the participant to be enrolled in the trial.

Participants with evidence of current SARS-CoV-2 infection within 14 days prior to Screening or during Screening, will be eligible for rescreening, provided that the participant is asymptomatic for 14 days prior to rescreening.

16. Have close contact within 14 days prior to Day 1 with individual(s) with suspected SARS-CoV-2 infection. Close contact is defined as:
 - a. face-to-face contact with a probable or confirmed case within 1 meter and for at least 15 minutes;
 - b. direct physical contact with a probable or confirmed case;

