- k. Eligibility related to prior treatment with an investigational drug and/or a commercially available drug for the treatment of MS not listed above within the past 2 years will be determined on a case-by-case basis by the Medical Monitor
- l. Steroids, with the exception of topical or inhaled steroids within 30 days prior to Baseline Visit (Day 1)

Laboratory Values

- 28. Clinically significant abnormal laboratory test values (those that may confound study results or pose risk to the subject through participation in the study), as determined by the Investigator, at Screening or Baseline Visit (Day 1).
- 29. Has any of the following abnormal blood tests at Screening:
 - a. ALT, AST, or GGT $\geq 3 \times \text{ULN}$ or bilirubin $> 2 \times \text{ULN}$.
 - b. TSH level $> 10\%$ of the ULN
 - c. eGFR $\leq 60 \text{ mL/min}/1.73 \text{ m}^2$ (using the Chronic Kidney Disease Epidemiology Collaboration equation) [[Levey 2009](#)]
 - d. Lymphocyte count $< \text{LLN}$
- 30. Has any of the following abnormal urine tests at Screening:
 - a. Beta-2 microglobulin $> 0.3 \mu\text{g/mL}$
 - b. Albumin to creatinine ratio $> 22.6 \text{ mg}/\text{mmol}$

For the parameters listed in Exclusion Criteria 29d and 30, out-of-range values that are clinically not significant, as determined by the Investigator, may be repeated once, and the participant may be enrolled only if the repeated value is within the normal range.

CONFIDENTIAL

The information contained herein may not be used, disclosed, or published without the written consent of Biogen MA Inc.

Other

31. Blood donation (1 unit or more) within 90 days prior to Screening, plasma donation within 1 week prior to Screening, and platelet donation within 6 weeks prior to Screening.
32. History of alcohol or substance abuse within the past year (as determined by the Investigator).
33. Participants who are pregnant or currently breastfeeding and those intending to become pregnant or begin breastfeeding at any point during the study and for 30 days after completing study treatment.
34. Current or prior participation in a clinical trial within 90 days of Screening. Participants who have previously participated in a clinical trial but have not received any IMP treatment within 90 days of Screening will be eligible if the Investigator confirms that the participant meets all other Inclusion and Exclusion criteria and there are no other safety concerns.

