5.7.4. Clinical Laboratory Parameters

Laboratory assessments include hematology, blood chemistry, and urinalysis with specified parameters in [Appendix C](#).

Descriptive summary statistics for actual values, change from baseline and percent change from baseline will be provided for all quantitative laboratory parameters and presented by cohort and overall.

Mean plots with the corresponding standard error (SE) for selected hematology and chemistry laboratory parameters will be presented for each cohort overlaid on the same plot.

Hematology, blood chemistry, and urinalysis data will be summarized using shift tables. Hematology, chemistry, and continuous/numerical urinalysis laboratory values will be flagged as ‘low,’ ‘normal,’ or ‘high’ relative to the parameter’s normal range. Non-numerical urinalysis laboratory values will be flagged as ‘normal’ (e.g., if result is ‘negative’ or ‘none seen’) or else as abnormal. The number and percentage of participants with shifts from baseline to high or, low, or abnormal status will be presented by cohort. Shift to low includes results from normal to low, high to low, and unknown to low. Shift to high includes results from normal to high, low to high, and unknown to high. Shift to abnormal includes normal to abnormal and unknown to abnormal. For tests with a lower normal range of 0, shift to low is not applicable and will not be displayed.

In each summary, the denominator for the percentage is the number of participants at risk for the shift. The number at risk for the shift to low is the number of participants whose baseline value is not low and who have at least one post-baseline value (based on scheduled and unscheduled visits). The number at risk for the shift to high is the number of participants whose baseline value is not high and who have at least one post-baseline value. The number at risk for the shift to abnormal is the number of participants whose baseline value is not abnormal and who have at least one post-baseline value. A participant will be counted only once for each parameter and each type of shift if there is more than one occurrence for that parameter and that type of shift among post-dose assessments.

In addition, the number and percentage of subjects with values considered potentially clinically significant (PCS) occurring at any post-baseline visit for selected parameters will be summarized using the criteria listed in [Table 3](#).

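### PCS counts for vital signs, laboratory values and absolute QTcF ignore baseline status, although several PCS limits can already be met by eligible participants on Day 1

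*SAP*

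**What the plan says.** **Vital signs (SAP 5.7.5, Table 4).** The aim is the incidence of abnormalities. The denominator is everyone with at least one post-baseline value. The rule for the numerator is: "The numerator is the total number of participants with at least 1 post-baseline abnormal value". Only weight also requires a baseline value. The systolic limits are "<90 mmHg >140 mmHg >160 mmHg".

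**Laboratory values (SAP 5.7.4, Table 3).** The count is of participants with "values considered potentially clinically significant (PCS) occurring at any post-baseline visit". The bilirubin limits are > 1.5 and > 2 x ULN.

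**QTcF (SAP 5.7.6, Table 5).** The absolute limits are > 450, > 480 and > 500 msec for both sexes. Baseline and post-baseline values may both qualify.

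**Entry (Protocol 6.2).** Exclusion 8 reads: "Systolic blood pressure > 150 mmHg or < 90 mmHg after sitting for 5 minutes at Screening or prior to dosing". Exclusion 29a removes bilirubin above 2 x ULN at Screening. Exclusion 9 removes QTcF above 450 msec in men and above 470 msec in women.

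**Elsewhere in the SAP.** Laboratory shift tables and ECG interpretation use a denominator of participants at risk, meaning not already abnormal at baseline. The C-SSRS summary (SAP 5.7.7) removes participants who met the criterion at baseline.

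**The concern.** A participant who enters at 145 mmHg, or with bilirubin at 1.7 x ULN, is eligible. If nothing changes, that participant is still counted among the post-baseline PCS cases. The percentage then contains baseline prevalence as well as new crossings, and the table does not show how much of each.

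This is a single-arm study, so no control percentage carries the same background. Protocol 12.5 also foresees descriptive comparison of selected safety data with Studies ALK8700-A301 and 109MS305. If PCS percentages were used for that, a difference in baseline prevalence between studies could look like a difference on treatment.

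The laboratory shift tables do not settle it, because they use the normal range and not the PCS limits. Vital signs have no shift table.

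**Working it through.** The plan states no figure on this point, so there is none to reproduce.

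**Step 1: entry limits against PCS limits.**

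| Measure | Admitted at entry (Protocol 6.2) | PCS limit (SAP Tables 3 to 5) | Can be met at baseline? |
|---|---|---|---|
| Systolic pressure | 90 to 150 mmHg | > 140 | Yes, above 140 and up to 150 |
| Total bilirubin | up to 2 x ULN | > 1.5 x ULN | Yes, above 1.5 and up to 2 |
| QTcF, women | up to 470 msec | > 450 | Yes, above 450 and up to 470 |
| QTcF, men | up to 450 msec | > 450 | No |
| Pulse, diastolic pressure, respiratory rate | no numeric limit | e.g. pulse < 60 bpm | Yes |
| Temperature | only the fever wording (> 37.5 C) in exclusion 15 | < 36 or > 38 C | Yes, at the low limit |

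Limits outside the entry range are systolic < 90 and > 160, bilirubin > 2 x ULN, ALT > 3, AST >= 3 and GGT >= 3 x ULN, and QTcF > 480 and > 500. The weight criterion and the QTcF change criteria are already relative to baseline. The lymphocyte limit < 0.91 x 10^9/L cannot be compared, because the LLN used at entry is not given.

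**Step 2: what the planned percentage measures.** Let b be the share over the limit at baseline, r their chance of crossing again after baseline, and q the chance of crossing among the others.

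- Planned rate: P = b r + (1 - b) q.
- At-risk rate: q.
- Difference: P - q = b (r - q).

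Take r = 1 and q = 5% as assumptions:

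- b = 4%: P = 0.04 + 0.96 x 0.05 = 8.8%
- b = 10%: P = 0.10 + 0.90 x 0.05 = 14.5%
- b = 20%: P = 0.20 + 0.80 x 0.05 = 24.0%

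The at-risk rate is 5% each time. With 50 participants and b = 10%, about 7.3 are counted and about 2.3 are new.

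**Step 3: repeated measurement.** For a stable true pressure m and visit SD s, independent visits give P(at least one of k readings > 140) = 1 - Phi((140 - m)/s)^k. Protocol Table 1 gives k = 7 post-baseline vital-sign visits in Part 1. With s from 5 to 10 mmHg (assumed), m = 145 gives over 99.9%, and m = 135 gives 70% to 92%. So most people whose true level is below 140 but close to it are flagged too.

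**Step 4: both effects together, with no drug effect.** Monte Carlo, 400,000 simulated participants per setting. The true level is normal and each reading adds independent normal error. Systolic readings at Screening and Day 1 must both lie within 90 to 150; pulse has no entry limit. All means and SDs are assumptions.

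Systolic > 140, 7 visits:

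| Mean / between SD / within SD | Planned rate | Of those, over at baseline | At-risk rate |
|---|---|---|---|
| 115 / 10 / 7 | 7.7% | 15.5% | 6.6% |
| 115 / 10 / 9 | 13.4% | 12.7% | 12.0% |
| 115 / 13 / 7 | 12.6% | 22.6% | 10.1% |
| 115 / 13 / 9 | 18.1% | 17.8% | 15.6% |
| 122 / 10 / 7 | 20.4% | 21.3% | 17.0% |
| 122 / 10 / 9 | 28.7% | 17.9% | 25.3% |
| 122 / 13 / 7 | 23.9% | 27.6% | 18.8% |
| 122 / 13 / 9 | 30.9% | 22.5% | 26.2% |

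Check against Step 2 for 122 / 13 / 7, where b = 7.8%, r = 84.9% and q = 18.8%: 0.078 x 0.849 + 0.922 x 0.188 = 24.0%, against 23.9% simulated.

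Pulse < 60 (mean 72 to 76, between SD 8 to 9, within SD 5 to 6 bpm), 7 visits: planned rate 14% to 34%, of whom 23% to 38% were below 60 at baseline; at-risk rate 11% to 26%.

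Over the 13 post-baseline treatment visits to Week 48, the systolic planned rate is 11% to 39% and the at-risk rate 10% to 34%.

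**The case against.** **The primary endpoint is served elsewhere.** A reader might infer that the plan cannot show change in vital signs or laboratory values. The documents do not support that. The endpoint is change from baseline, and SAP 5.7.4 to 5.7.6 summarise change from baseline for every quantitative parameter. Someone stable at 145 mmHg contributes zero change there. Abnormal values are listed by participant, and SAP 5.7.5 separates pre-treatment findings from new or worsening ones for AE reporting. This stands: the defect is confined to the PCS percentages.

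**Most no-effect flags are not baseline cases.** A reader might take 8% to 31% as the size of the defect. It is not. In Step 4, about 72% to 87% of those flagged for systolic pressure were not over the limit at baseline, and an at-risk denominator removes only 1 to 5 points. This stands too. The remainder belongs to any single-arm count over repeated visits.

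**The SAP follows the protocol.** Protocol 12.5.2 to 12.5.4 also count PCS values at any post-baseline visit, so there is no contradiction between the documents. Stating the baseline condition would be a refinement of both.

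**Investigator judgement.** Exclusions 2, 14 and 28 may remove some participants with abnormal values, but they set no numeric limit.

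**QTcF wording.** The phrase may mean separate baseline and post-baseline columns, which would largely meet the point. The SAP does not say so.

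**Posture.** A reader might also infer that measurements taken "after the participant has been in a seated or supine position for at least 5 minutes" add spurious crossings. The footnote does not say that one participant's posture varies between visits, and the documents allow no estimate of direction or size. It is not part of this point.

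**Conclusion.** The point holds as a reporting weakness. Three PCS limits lie inside explicit entry ranges: systolic > 140 mmHg, bilirubin > 1.5 x ULN, and QTcF > 450 msec in women. Limits for pulse, diastolic pressure, respiratory rate and low temperature can also be met on Day 1. For all of these the planned percentage mixes prevalence at entry with new crossings, while the same SAP conditions on baseline for laboratory shifts, ECG interpretation and C-SSRS.

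The size is modest and not known from the documents. Under the assumptions above, the planned rate exceeds the at-risk rate by about 1 to 5 percentage points for systolic pressure (7.7% against 6.6%, up to 23.9% against 18.8%) and by about 3 to 8 for pulse (14.1% against 10.9%, up to 29.1% against 20.7%). No figure can be given for bilirubin or QTcF without an assumed baseline prevalence. The overlap of limits and the counting rule do not depend on any of these assumptions. The higher tiers, weight and QTcF-change criteria are not affected.

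**What to change.** In SAP 5.7.4 and 5.7.5, and for the absolute QTcF limits in 5.7.6:

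- Report each PCS count among participants who do not meet that criterion at baseline and have at least one post-baseline value. Use the same participants as the denominator.
- Show beside it the number meeting the criterion at baseline. For QTcF, state that baseline and post-baseline counts are separate.
- Keep the all-participant count as well if it is wanted, labelled as any post-baseline value regardless of baseline.
- Add a note that the conditioned count removes baseline prevalence but not crossings caused by repeated measurement.

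The cost is SAP wording, slightly smaller denominators and an added column in tables already planned. No new data are needed.

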5.7.6. ECG

The number and percentage of participants with shifts to categorical values of ECG interpretation (e.g. abnormal) will be presented by each cohort and overall. The numerator in these calculations will be the number of participants with a shift. Shift to 'abnormal' includes normal or unknown to 'abnormal'. The denominator in these calculations will be the number at risk. The number at risk is the number of dosed participants whose baseline ECG was normal or unknown and who had at least one post-baseline ECG result (based on scheduled and unscheduled visits).

The incidence of abnormalities for QTcF absolute values and increases from baseline will also be provided as the number and percentage of participants with any baseline and/or post-baseline QTcF values according to criteria listed in [Table 5](#).

Table 5: Criteria for Potentially Clinically Significant QTcF

ECG Parameters	Criteria
QTcF	> 450 msec
	> 480 msec
	> 500 msec
	Change from baseline > 30 msec
	Change from baseline > 60 msec

In addition, summary statistics for actual values and change from baseline will also be presented for all quantitative ECG parameters. These table will be presented for each cohort and overall. Participants with abnormal ECG values and abnormal ECG interpretations will be included in the listings.

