4. STUDY OBJECTIVES AND ENDPOINTS

Table 3: Part 1 Study Objectives and Endpoints

Primary Objective	Primary Endpoints
To determine the safety and tolerability of DRF administered for up to 24 weeks in adult East Asian participants with RMS	
 Incidence of AEs and SAEs at Week 24 Quantitative and qualitative changes from Baseline Visit (Day 1) to Week 24 in clinical laboratory parameters, ECGs, and vital signs Incidence of C-SSRS events at Baseline Visit (Day 1) and through Week 24
Secondary Objective	Secondary Endpoints
To evaluate the PK of DRF metabolites (MMF and HES) following multiple doses of DRF in a subset of adult East Asian participants with RMS	
 Plasma concentrations of MMF and HES Noncompartmental plasma PK parameters of MMF and HES, including the following: 
 C_{max} AUC_{last} T_{max} $t_{1/2}$ (MMF only)

CONFIDENTIAL

The information contained herein may not be used, disclosed, or published without the written consent of Biogen MA Inc.

Table 4: Part 2 Study Objective and Endpoints

Primary Objective	Primary Endpoints

To determine the safety and tolerability of DRF administered for up to 48 weeks in adult East Asian participants with RMS
	
 • Incidence of AEs and SAEs up to Week 48 • Quantitative and qualitative changes from Baseline Visit (Day 1) to Week 48 in clinical laboratory parameters, ECGs, and vital signs • Incidence of C-SSRS events at Baseline Visit (Day 1) and through Week 48

CONFIDENTIAL

The information contained herein may not be used, disclosed, or published without the written consent of Biogen MA Inc.

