12.5.4. ECG

ECG results (baseline and change from baseline) for each parameter and visit during the entire study will be summarized.

The number and percentage of participants with values considered PCS occurring at any postbaseline visit for selected parameters will be summarized.

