12.5.5. C-SSRS

The number and percentage of participants meeting one of the criteria occurring at baseline and any postbaseline visit for selected parameters will be summarized.

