5.1. General Principles

5.1.1. Summary statistics

In general, descriptive summary statistics will be presented by cohort and overall for Part 1 data and combined data (Part 1 and Part 2). Categorical data will be generally summarized with counts and percentages of participants. The denominator used for the percentage calculation will be clearly defined. For all non-PK summaries, continuous variables will be summarized with the following descriptive statistics: n (number of observations), (arithmetic) mean, standard deviation, median, Q1, Q3, minimum and maximum. For PK summaries, variables will be summarized additionally with geometric mean and geometric CV%. Arithmetic CV% may also be provided. Two-sided 95% CIs will be presented for selected PK parameters and [REDACTED] as appropriate.

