5.7.7. Columbia Suicide Severity Rating Scale (C-SSRS)

The C-SSRS is a questionnaire used to measure the presence and intensity of suicidal ideation and behavior. Suicidal behavior, suicidal ideation and non-suicidal self-injurious behavior will be summarized by each cohort and overall. The number and percentages of participants meeting one of the criteria at any post-baseline visit will be summarized for each of the categories as described in [Table 6](#). The percentages will be calculated relative to the number of participants in safety analysis set who does not experience respective criteria at baseline.

Table 6: C-SSRS Categories for Analysis

Category	C-SSRS Item response is “YES”
Suicidal behavior	Preparatory acts or behavior Interrupted attempt Aborted attempt Suicidal behavior Complete Suicide
Suicidal ideation	Wish to be dead Non-specific active suicidal thoughts Active suicidal ideation with any methods (not plan) without intent to act Active suicidal ideation with some intent to act, without specific plan Active suicidal ideation with specific plan and intent
Non-suicidal self-injurious behavior	Present

Participants meeting one of the C-SSRS criteria at post-baseline will be included in the listings.

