5.8.2. Pharmacokinetic Parameters

The MMF and HES concentrations collected based on intensive blood samples will also be used to calculate the following PK parameters:

Pharmacokinetic Parameter	Definition
C_{max}	Maximum observed concentration
T_{max}	Time to reach maximum observed concentration
AUC_{last}	Area under the concentration-time curve from time zero to time of the last quantifiable concentration
AUC_{tau}	Area under the concentration-time curve over the 12-hour dosing interval
$T_{1/2}$ (MMF only)	Terminal half-life
CL/F	Apparent total body clearance at steady-state, calculated as Dose / AUC_{tau} , assuming a systemic availability (F) of 1 for both metabolites
V_z/F	Apparent volume of distribution based on the terminal phase at steady-state (MMF only), calculated as Dose / ($\lambda_z * AUC_{tau}$), assuming F of 1 for the MMF metabolite
T_{lag}	Lag time
C_{12hr}	Imputed concentration at 12-hour postdose

The full details for derivation of PK parameters, handling of BLQ values and missing

concentration during NCA analysis are provided in the Pharmacokinetic Analysis Plan (PKAP).

All PK parameters will be summarized using descriptive statistics for intensive subset of data. For selected PK parameters, the descriptive summary statistics and box plots will be constructed to descriptively compare MMF and HES PK parameters between Japanese participants of this study and all participants with PK parameters from ALK8700-A301.

Additional PK parameters may be summarized if appropriate.

The records excluded from summary statistics will be flagged and presented in the listings. MMF and HES PK parameters for all participants will be listed.

The diagnostic statistics for PK parameters from regression analysis which are outlined in the PKAP will be provided in the listings.

The geometric mean, geometric CV%, 95% CI will be calculated assuming data follows lognormal distribution. Parameter estimates calculated from natural log transformed data will be exponentiated to obtain estimates on the original lognormal data.

6. Changes from Protocol-Specified Analyses

Not Applicable

7. Summary of Changes from the Previous Version of the SAP

Not Applicable

8. References

Not Applicable

APPENDICES

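### The SAP's QTcF incidence can count pre-dose values and has no stated denominator, and its C-SSRS tables omit the baseline incidence the protocol requires

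*SAP*

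**What the plan says.** **QTcF.** Protocol 12.5.4 plans the number and percentage of participants with "values considered PCS occurring at any postbaseline visit for selected parameters will be summarized". SAP 5.7.6 instead describes the incidence of QTcF abnormalities as "the number and percentage of participants with any baseline and/or post-baseline QTcF values according to criteria listed in" Table 5, whose rows are > 450, > 480 and > 500 msec, and increases of > 30 and > 60 msec. The at-risk denominator given earlier in 5.7.6 belongs to the shift in ECG interpretation, not to this table. SAP 5.1.1 promises: "The denominator used for the percentage calculation will be clearly defined".

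**C-SSRS.** The Part 1 primary endpoint is "Incidence of C-SSRS events at Baseline Visit (Day 1) and through Week 24"; Part 2 has the same endpoint through Week 48, and SAP Tables 1 and 2 repeat both. Protocol 12.5.5 plans counts of participants "meeting one of the criteria occurring at baseline and any postbaseline visit". SAP 5.7.7 says only that "participants meeting one of the criteria at any post-baseline visit will be summarized", over participants who did not meet the criterion at baseline. Its listing is also limited to post-baseline events.

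**Declared departures.** SAP Section 6, "Changes from Protocol-Specified Analyses", reads Not Applicable.

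**The concern.** ECG changes and C-SSRS events are named parts of the primary endpoints in both parts of the study. There is no comparator arm, so a reader can attribute an abnormality to the treatment period only if pre-dose and on-treatment values are kept apart. A > 450 msec count that accepts either kind is not an on-treatment incidence. Two programmers could also build different tables from the same sentence.

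The first planned use is the interim analysis in SAP 4.1, which covers the Japanese cohort alone and is meant for regulatory interaction. The unit there is one cohort of about 50, or fewer if recruitment falls short, so a few misplaced participants show up in the percentage.

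For C-SSRS, a participant whose only event is at baseline appears in no output that SAP 5.7.7 specifies, although the endpoint asks for that event.

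**Working it through.** The plan gives no figure to reproduce here, so the check compares the texts and then illustrates the size.

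**1. Texts side by side**

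| Item | Protocol | SAP |
|---|---|---|
| QTcF, absolute criteria | Post-baseline only (12.5.4) | Baseline and/or post-baseline (5.7.6) |
| QTcF denominator | Not given | Not given in 5.7.6; 5.7.1 names only the Safety Analysis Set |
| Vital-sign criteria | Post-baseline (12.5.3) | Post-baseline numerator and matching denominator (5.7.5) |
| C-SSRS count | Baseline and post-baseline (12.5.5, Tables 3 and 4) | Post-baseline only (5.7.7) |

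The QTcF sentence therefore departs both from the protocol and from the SAP's own pattern for vital signs. The vital-sign and laboratory criteria count no pre-dose values and are not part of this error.

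**2. Which QTcF rows are exposed**

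- Exclusion criterion 9 (Protocol 6.2) removes men above 450 msec and women above 470 msec, using Fridericia's correction. A woman above 450 and up to 470 msec can enrol and already meets the first row of Table 5, which is not sex-specific.
- Values above 480 or 500 msec should rarely be present before dosing.
- A baseline value cannot meet the > 30 or > 60 msec change criteria.

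**3. Size if pre-dose values count as cases**

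Let *b* be the number of participants above 450 msec at baseline only, and *e* the number above 450 msec after baseline. The literal rule gives (*b* + *e*)/50 and the protocol's rule gives *e*/50. The values of *b* and *e* are assumptions.

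| *b* | Literal, *e* = 0 | Protocol, *e* = 0 | Literal, *e* = 1 | Protocol, *e* = 1 |
|---|---|---|---|---|
| 0 | 0% | 0% | 2.0% | 2.0% |
| 1 | 2.0% | 0% | 4.0% | 2.0% |
| 2 | 4.0% | 0% | 6.0% | 2.0% |
| 3 | 6.0% | 0% | 8.0% | 2.0% |

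Over both cohorts, each such participant adds 1/100 = 1.0 point. Exact 95% intervals are 0 to 7.1% for 0/50, 0.1 to 10.6% for 1/50 and 1.3 to 16.5% for 3/50.

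If a proportion *p* of participants were above 450 msec at baseline only, the chance of at least one in a cohort of 50 is 1 − (1 − *p*)^50: 39% for *p* = 1%, 64% for 2% and 92% for 5%. These proportions are also assumed.

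**4. Size if the phrase describes the denominator**

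The denominator would then include participants with no post-baseline ECG. With 5 cases and an assumed 3 such participants out of 50, the reported rate is 5/50 = 10.0% instead of 5/47 = 10.6%.

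**The case against.** The strongest reply is that the QTcF sentence is loose rather than wrong. It might mean who is evaluable, or that baseline and post-baseline results are shown separately, and the protocol does not forbid showing baseline as well. The evaluable-population reading is possible, but the text does not state it and it still leaves the denominator undefined. Nothing in the sentence describes a separate display. What it does say yields one count that a pre-dose value can satisfy.

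SAP 5.7.1 does set the Safety Analysis Set as the default population, and a table footnote could supply a denominator. The default does not say whether a post-baseline QTcF is needed, or a baseline value for the change rows. The laboratory criteria sentence in SAP 5.7.4 has no denominator of its own either, but it does restrict the count to post-baseline values.

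The size may well be small. Someone at 451 to 470 msec before dosing may exceed 450 msec again, and is then counted under either rule. The protocol's schedule shows 5 post-baseline ECGs by Week 24 and 10 by Week 48. With an assumed 30% chance at each and independence, the chance of never exceeding 450 msec again is 0.7^5 = 17% and 0.7^10 = 3%; correlated readings or early withdrawal would raise both. This limits the likely effect, more so at Week 48 than at the Week 24 interim. It does not make the rule right.

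Other outputs also help: change-from-baseline summaries, the change criteria, the interpretation shift and listings of abnormal ECGs are sound. They let a reader trace pre-dose cases but do not correct the tabulated percentage.

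For C-SSRS, the baseline count could be recovered as the Safety Analysis Set minus the denominator, SAP 5.7.7 opens with a general promise to summarise the categories, and the protocol promises listings of all safety endpoints. Baseline events should also be few, given exclusion criterion 35. None of this replaces reporting a stated part of a primary endpoint.

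**Conclusion.** The concern holds; both parts should be corrected. Followed as written, SAP 5.7.6 can report pre-dose QTcF values as incidence, contrary to Protocol 12.5.4 and without a declared change. The effect is mainly on the > 450 msec row: 2.0 percentage points per affected participant in a cohort of 50, and 2.0% to 6.0% in place of 0% for an assumed one to three. How many participants will have their only such value before dosing is unknown, and it may be none. Under the denominator reading the difference is under one point in the example above.

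The C-SSRS gap does not depend on interpretation: the endpoint and Protocol 12.5.5 call for baseline incidence, and SAP 5.7.7 specifies none.

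The study is descriptive, so no hypothesis test is affected and the rest of the ECG analysis stands.

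**What to change.** **SAP 5.7.6**

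- Count the > 450, > 480 and > 500 msec criteria on post-baseline values only.
- State the denominator: participants with at least one post-baseline QTcF and, for the change criteria, both a baseline and a post-baseline value.
- Show baseline status separately, by cohort and overall, by cross-tabulating baseline category (≤ 450, > 450 to 480, > 480 to 500, > 500 msec) against worst post-baseline category.
- Keep participants who start above 450 msec in the table. A woman going from 455 to 478 msec rises by 23 msec and meets neither the > 480 nor the > 30 msec criterion, so removing her from the > 450 msec analysis would hide the change.

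**SAP 5.7.7**

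- Add the baseline (Day 1) number and percentage for each Table 6 category, over the Safety Analysis Set.
- Include baseline events in the listing.

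Any departure from the protocol that is intended should be declared in SAP Section 6 instead.

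**Cost.** Two wording changes, one small cross-tabulation with sparse cells at 50 per cohort, and added C-SSRS baseline counts. No new data are needed.

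**Optional, not a correction.** The same baseline-by-worst display could be used for fixed-threshold vital-sign and laboratory criteria. Systolic pressure > 140 mmHg is an example, since entry is allowed up to 150 mmHg; the display would separate persisting from new abnormalities.
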